5.3 Screening Failures

Patients who signed the ICF but were found not eligible for the study prior to receiving study drug are defined as screening failures.

For these patients, only limited information will be collected in the electronic case report form (eCRF):

- Informed consent
- Demographics
- Inclusion/exclusion criteria
- SAE and/or death occurring during the Screening Period
- Screening failure details

5.4 Re-screening Procedures

A patient who did not meet the eligibility criteria (screening failure) may be considered for re-screening. Decision for re-screening must be confirmed by the Sponsor/Medical monitor. A re-screened patient should be assigned a new patient number.

5.5 Discontinuation

The reason for discontinuation and the date of discontinuation will be collected for all patients.

Note: Once discontinued from the study for any reason, patients are not permitted to be re-enrolled.

5.5.1 Discontinuation from Study Drug

A patient may be discontinued from the study drug for any of the following reasons:

- Planned for HSCT
- Major protocol deviation
- Discontinuation of the study by the Sponsor

A patient must be discontinued from the study drug for any of the following reasons:

- Investigator's decision
- Patient decision
- Disease progression (radiographic and/or clinical) based on Investigator's assessment
- Unacceptable toxicity
- Pregnancy
- Death

IMPORTANT: Study drug discontinuation is not to be automatically considered as withdrawal from the study. Patients discontinuing the study drug will be asked to perform an EOT visit (Section 4.2.3) and continue with the Follow-up period (Section 4.2.4) as per protocol.

The investigational site should make every effort to complete follow-up per protocol. If patients are unable to return to the site, patient status (including, but not limited to, survival status) may be obtained by site staff via phone, email, or mail.

5.5.2 Discontinuation from the Study

A patient may be discontinued from the study for any of the following reasons:

- Withdrawal of consent
- Investigator/Sponsor decision
- Death
- Loss to follow-up (Section 5.5.3)
- Study completion

If a patient withdraws informed consent for the study, no additional study data will be collected. The Sponsor may continue to use previously collected medical research data prior to the withdrawal consistent with the original authorization.

The study may be terminated at any time, for any reason, by the Sponsor. Patients still receiving study drug should have an EOT visit as described in Section 4.2.3 and Schedule of Events (SoE) (Table 1).

5.5.3 Loss to Follow-up

Patients who fail to return for protocol follow-up are to be contacted by the investigative site. Following a minimum of two documented unsuccessful telephone calls, the investigative site should send a registered letter to the patient in a final attempt to ensure protocol compliance.

5.6 Patient Replacements

No patients will be replaced.

6 Treatment

6.1 Study Drug

Camidanlumab tesirine will be provided as a lyophilized white to off-white powder in 2 mL glass vials (5 mg camidanlumab tesirine per vial) and stored at 2°C to 8°C. The lyophilized camidanlumab tesirine is formulated in 20 mM histidine, 175 mM sucrose, and 0.04% polysorbate 20, at pH 6.0. Prior to use, the study drug is reconstituted with 1.2 mL of sterile water for injection to deliver 1.0 mL at a concentration of 5 mg/mL. After reconstitution, the vial should be gently swirled (do not shake the vial) to ensure complete dissolution and homogeneity, and visually inspected prior to use. Sterile water for injection is to be provided by study sites.

Additional study drug description is included in the pharmacy manual.

6.2 Management of Clinical Supplies

Detailed instructions regarding study drug shipment, handling, storage, preparation, and administration are included in the pharmacy manual.

6.2.1 Packaging and Storage

The study drug will be supplied by the Sponsor through the designated packaging, labeling, and distribution center.

All study drugs must be stored according to the pharmacy manual, in a secure area.

The lyophilized formulation of camidanlumab tesirine should be protected from long-term exposure to light and stored refrigerated (2°C to 8°C). Light protection is not required for dose preparation and during administration of the diluted drug in the IV bag.

6.2.2 Preparation and Administration

The study drug solution at a concentration of 5 mg/mL will be the basis for the preparation of the infusion solution. The amount of the product to be diluted will depend on the dose level and the body mass of the patient. Of note, a cap on the administered dose is to be applied for patients with a body mass index \geq 35 kg/m². Additional details are included in the pharmacy manual.

Administration of camidanlumab tesirine will be performed by the Investigator or a qualified designee according to the pharmacy manual.

Camidanlumab tesirine is administered as a 30-minute intravenous (IV) infusion on Day 1 of each cycle.

Variations in infusion times due to minor differences in IV bag overfill/underfill and the institution's procedure for flushing chemotherapy lines will not result in protocol deviation.

Extravasation of camidanlumab tesirine may be associated with local irritation, swelling, pain, or tissue damage. The IV infusion site should be monitored for signs of IV infiltration or drug extravasation, and patients should be instructed to report immediately any signs of IV infiltration or drug extravasation during or after the infusion. Suspected extravasation of camidanlumab tesirine should be managed according to institutional protocol for management of extravasation of cytotoxic chemotherapy.

For patients who have a central line, administration of camidanlumab tesirine via this central line should be considered.

6.2.3 Accountability

The Investigator or designee will maintain accurate records of receipt of all study drugs, including dates of receipt. In addition, accurate records will be kept regarding when and how much study drug is dispensed and used by each patient in the study. Reasons for departure from the expected dispensing regimen must also be recorded. All study drugs will be reconciled and retained or destroyed according to applicable regulations.

6.3 Camidanlumab Tesirine Dosing

Camidanlumab tesirine will be administered at a dose of 45 μ g/kg Q3W for 2 cycles, then 30 μ g/kg for subsequent cycles.

Refer to Section 6.7 for premedication and supportive care.

6.4 Dose Delays and Modifications

The Investigator may suspend camidanlumab tesirine dosing for up to 21 days, for any patient who experiences any toxicity of any grade.

Resumption of dosing with camidanlumab tesirine after any suspension, even when longer than 21 days, is at the discretion of the Investigator, on assessment of the patient's clinical condition and whether or not the patient is deriving potential clinical benefit from treatment with camidanlumab tesirine.

The Investigator may also suspend camidanlumab tesirine dosing for any patient scheduled for HSCT in the near future, and resumption of dosing is only allowed if the patient has not received in the meantime any chemotherapy-based mobilization/conditioning therapy or HSCT.

Management of toxicities, when considered to be at least possibly related to camidanlumab tesirine, must be performed according to:

- Section 6.4.1 for general events (i.e., not specified in the below sections),
- Section 6.4.2 for specific non-hematologic events,
- Section 6.4.3 for specific hematologic events,
- Section 6.4.4 for specific neurologic events,

• Section 6.4.5 for specific skin events.

6.4.1 Guidelines for Dose Modification: General

AE Grade	Camidanlumab Tesirine Management Guideline			
1/2	No dose adjustment is required.			
3/4	First Occurrence:			
	 Hold camidanlumab tesirine until improvement to ≤ Grade 1 or Baseline. 			
	• If improvement to ≤ Grade 1 or Baseline occurs prior to the next scheduled dose, proceed with the originally planned camidanlumab tesirine dose level.			
	• If improvement to ≤ Grade 1 or Baseline occurs > 21 days from the last scheduled (but missed) camidanlumab tesirine dose, continue camidanlumab tesirine and reduce from 45 to 30 μg/kg or from 30 to 20 μg/kg.			
	Second Occurrence:			
	• Hold camidanlumab tesirine until improvement to ≤ Grade 1 or Baseline, reduce from 45 to 30 μg/kg or from 30 to 20 μg/kg.			
	Third Occurrence:			
	Permanently discontinue camidanlumab tesirine.			

6.4.2 Guidelines for Dose Modification: Specific Non-hematologic Toxicities

Adverse Event	Grade	Camidanlumab Tesirine Management Guideline
Infusion-related reactions	1	The infusion rate may be decreased or temporarily interrupted to permit resolution of the event. If the total time for dilution into the IV bag and infusion takes longer than 4 hours, the remaining solution of camidanlumab tesirine will be discarded and the dosing will continue with the assigned dose at the next scheduled dosing visit. Please refer to Section 6.7.3 for treatment recommendation.
	2	Interrupt camidanlumab tesirine infusion to permit resolution of the event. If the event resolves within the total time of 4 hours after dilution into the IV bag and infusion time, resume camidanlumab tesirine infusion at 50% of the prior infusion rate, still not exceeding the total of 4 hours after infusion has restarted.
		If the resolution takes longer than the total 4 hours, the remaining solution of camidanlumab tesirine will be discarded, and the dosing will continue with the assigned dose at the next scheduled dosing visit at 50% of the prior infusion rate. Please refer to Section 6.7.3 for treatment recommendation.
	3	Permanently discontinue camidanlumab tesirine. However, if the AE resolves within 24 hours after onset (with or without clinical management), dosing may continue with the assigned dose at the next scheduled dosing visit at 50% of the prior infusion rate.
		Please refer to Section 6.7.3 for treatment recommendation.
	4	Permanently discontinue camidanlumab tesirine.
AST, ALT, or GGT abnormalities	2/3	 First Occurrence: Hold camidanlumab tesirine until improvement to ≤ Grade 1 or Baseline. If improvement to ≤ Grade 1 or Baseline occurs prior to
Edema		the next scheduled dose, proceed with the originally planned camidanlumab tesirine dose level.
or Effusion		 If improvement to ≤ Grade 1 or Baseline occurs > 21 days from the last scheduled (but missed) camidanlumab tesirine dose, reduce from 45 to 30 μg/kg or from 30 to 20 μg/kg.
		Second Occurrence:
		 Hold camidanlumab tesirine until improvement to ≤ Grade 1 or Baseline.
		• If improvement to ≤ Grade 1 or Baseline occurs, reduce from 45 to 30 μg/kg or from 30 to 20 μg/kg.

Adverse Event	Grade	Camidanlumab Tesirine Management Guideline	
		Third Occurrence:	
		Permanently discontinue camidanlumab tesirine.	
	4	First Occurrence:	
		 Hold camidanlumab tesirine until improvement to ≤ Grade 1 or Baseline. 	
		 If improvement to ≤ Grade 1 or Baseline occurs, continue camidanlumab tesirine and reduce from 45 to 30 µg/kg or from 30 to 20 µg/kg. 	
		Second Occurrence:	
		Permanently discontinue camidanlumab tesirine.	
Hy's law (AST and/or	-	Permanently discontinue camidanlumab tesirine.	
ALT > 3 × ULN and bilirubin > 2 × ULN)		Hy's law defined as: AST and/or ALT $> 3 \times$ ULN and bilirubin $> 2 \times$ ULN, and without initial findings of cholestasis (ALP activity $< 2 \times$ ULN) and no other reason that could explain the combination of increased transaminases and serum total bilirubin, such as viral hepatitis A, B, or C, preexisting or acute liver disease, or another drug capable of causing the observed injury.	
Autoimmune toxicities (e.g., hyperthyroidism, hypothyroidism, hepatitis, other endocrinopathies)	≥1	Need to be followed at least weekly to quickly detect deterioration and modify dosing as per general recommendations in Section 6.4.1 (can be done by telephone unless symptoms worsen). Consider using ASCO guidelines for management of immunemediated toxicities (Brahmer, 2018), or local guidelines.	
		Specific guidelines for management of hyperthyroidism, hypothyroidism, and hepatitis are provided in the Appendix 13.5.	
Selected Types of Infection: HSV1, HSV2, VZV, EBV, CMV, measles, Influenza A, Zika virus, Chikungunya virus, mycoplasma pneumonia, Campylobacter jejuni, enterovirus D68, or SARS-CoV-2.	Any Grade	No dose adjustment is required; however, hold camidanlumab	

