^{*} A score of 3 in many patients indicates a good prognosis with standard treatment, especially if at the time of an interim scan. However, in trials involving PET where de-escalation is investigated, it may be preferable to consider a score of 3 as inadequate response (to avoid undertreatment). Measured dominant lesions: Up to six of the largest dominant nodes, nodal masses, and extranodal lesions selected to be clearly measurable in 2 diameters. Nodes should preferably be from disparate regions of the body and should include, where applicable, mediastinal and retroperitoneal areas. Non-nodal lesions include those in solid organs (e.g., liver, spleen, kidneys, lungs), GI involvement, cutaneous lesions, or those noted on palpation. Nonmeasured lesions: Any disease not selected as measured, dominant disease and truly assessable disease should be considered not measured. These sites include any nodes, nodal masses, and extranodal sites not selected as dominant or measurable or that do not meet the requirements for measurability but are still considered abnormal, as well as truly assessable disease, which is any site of suspected disease that would be difficult to follow quantitatively with measurement, including pleural effusions, ascites, bone lesions, leptomeningeal disease, abdominal masses, and other lesions that cannot be confirmed and followed by imaging. In Waldeyer's ring or in extranodal sites (e.g., GI tract, liver, bone marrow), FDG uptake may be greater than in the mediastinum with complete metabolic response, but should be no higher than surrounding normal physiologic uptake (e.g., with marrow activation as a result of chemotherapy or myeloid growth factors).

^{**} PET 5PS: 1, no uptake above background; 2, uptake ≤ mediastinum; 3, uptake > mediastinum but ≤ liver; 4, uptake moderately > liver; 5, uptake markedly higher than liver and/or new lesions; X, new areas of uptake unlikely to be related to lymphoma.

13.5 Appendix: Management of Specific Autoimmune Toxicities: Hyperthyroidism, Hypothyroidism, and Hepatitis

Adverse Event	Grade	Camidanlumab Tesirine Management Guideline
Hyperthyroidism	1	No dose adjustment is required.
V V		Close follow-up (at least weekly; by phone if stable) and monitoring of TSH, reflex FT4 and/or FT3 (as applicable), every 2-3 weeks, until it is clear whether there will be persistent hyperthyroidism (>6 weeks) or hypothyroidism.
	2	Consider endocrine consultation.

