		Dose delay is at the Investigator's discretion. Rechallenge without dose adjustment is permitted.
		β-blocker (e.g., atenolol) for symptomatic relief, hydration, and supportive care may be needed.
		For persistent hyperthyroidism or clinical suspicion (e.g., ophthalmopathy or thyroid bruit), work-up for Graves disease and consider thionamide.
	3/4	Endocrine consultation is indicated.
		Hold camidanlumab tesirine until improvement to \leq Grade 1 or Baseline with appropriate therapy. Rechallenge is then permitted as per General Guidelines for Dose Modification (Section 6.4.1).
		Give β-blocker (e.g., atenolol) for symptomatic relief.
		For severe symptoms or concern for thyroid storm, hospitalize patient and initiate prednisone 1-2 mg/kg/day or equivalent tapered over 1-2 weeks; consider also use of saturated solutions of potassium iodide or thionamide.
Hypothyroidism	1	Asymptomatic; TSH generally <10 mIU/L.
		No dose adjustment is required.
		Close follow-up (at least weekly; by phone if stable) and monitoring of TSH, FT4/FT3 (as applicable) every 4-6 weeks.
	2	TSH generally persists >10 mIU/L.
		Consider endocrine consultation.
		Dose delay is at the Investigator's discretion. Rechallenge without dose adjustment is permitted.
		Give thyroid hormone supplementation in symptomatic patients with any degree of TSH elevation or in asymptomatic patients with TSH levels that persist >10 mIU/L.
		Monitor TSH, FT4/FT3 (as applicable) every 6-8 weeks while titrating hormone replacement to normal TSH. Thereafter, monitor TSH, FT4 and/or FT3 (as applicable) every 6 weeks during camidanlumab tesirine treatment or as needed for symptoms to ensure appropriate hormone replacement; repeat testing annually or as indicated by symptoms once stable.

Adverse Event	Grade	Camidanlumab Tesirine Management Guideline
	3/4	Endocrine consultation is indicated.
		Hold camidanlumab tesirine until improvement to ≤ Grade 1 or Baseline, or control with appropriate supplementation. Rechallenge is then permitted as per General Guidelines for Dose Modification (Section 6.4.1).
		May admit for IV therapy if signs of myxedema (bradycardia, hypothermia)
		Provide thyroid supplementation and reassessment as in Grade 2.
Hepatitis	1/2	Asymptomatic LFT elevations and Hy's law should be managed per guidances given in the Section 6.4.2.

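### Section 6.4.2 sends autoimmune hepatitis dosing to the general rules, which allow re-treatment after Grade 3/4; Appendix 13.5 requires a permanent stop, and no sentence says which prevails.

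*Protocol*

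**What the plan says.** Section 6.4 of the Protocol directs toxicities at least possibly related to study drug to Sections 6.4.1 to 6.4.5. It describes the scope of the first of these as "Section 6.4.1 for general events (i.e., not specified in the below sections". Appendix 13.5 is not on that list.

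The autoimmune-toxicities row of Section 6.4.2 applies from Grade 1 upward and gives hepatitis as one of its examples. Its dosing instruction is "modify dosing as per general recommendations in Section 6.4.1". The same cell then adds: "Specific guidelines for management of hyperthyroidism, hypothyroidism, and hepatitis are provided in the Appendix 13.5".

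For Grade 3/4 events, Section 6.4.1 works by occurrence:

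- **First occurrence:** hold. If recovery comes before the next scheduled dose, "proceed with the originally planned camidanlumab tesirine dose level"; if it comes more than 21 days after the missed dose, resume one dose level lower.
- **Second occurrence:** "Hold camidanlumab tesirine until improvement to ≤ Grade 1 or Baseline, reduce from 45 to 30" µg/kg, or from 30 to 20.
- **Third occurrence:** stop permanently.

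For Grade 3/4 hyperthyroidism and hypothyroidism, Appendix 13.5 sends the reader back to these rules: "Rechallenge is then permitted as per General Guidelines for Dose Modification (Section 6.4.1"). For hepatitis it orders permanent discontinuation at Grade 3 and, in a separate row, at Grade 4. It counts no occurrences and does not return to 6.4.1.

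**The concern.** One table row leads to two different answers for the same event. A site that takes its dosing decision from the first pointer may re-treat after Grade 3 or 4 autoimmune hepatitis. A site that goes on to the appendix may not. The row ties dosing to 6.4.1 and management to the appendix, so a reader could use the appendix for work-up and steroids and still take the dosing decision from 6.4.1.

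The protocol's other permanent stops of this kind are easier to find. The stop for Hy's law is written in 6.4.2 and the stop for Guillain-Barré syndrome in 6.4.4. The hepatitis stop appears only in the appendix. Section 5.5.1 makes unacceptable toxicity a mandatory reason to discontinue but names no events, so it does not settle the matter.

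At stake is patient safety and, secondarily, deviation reporting. Item 3 of SAP Section 4.3 counts patients who met a mandatory withdrawal criterion and stayed on drug. Whether re-treatment after Grade 3/4 hepatitis belongs in that count should not depend on which half of the row is read.

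**Working it through.** The plan gives no figure to reproduce. The check sets the instructions side by side.

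| Event, Grade 3 or 4 | 6.4.2 row, via 6.4.1 | Appendix 13.5 | Same answer on rechallenge? |
|---|---|---|---|
| Hyperthyroidism | Hold, then resume after events 1 and 2 | Hold, then rechallenge per 6.4.1 | Yes |
| Hypothyroidism | Hold, then resume after events 1 and 2 | Hold, then rechallenge per 6.4.1 | Yes |
| Hepatitis | Hold, then resume after events 1 and 2 | Permanent stop at Grade 3 and at Grade 4 | No |

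For hypothyroidism the appendix also releases the hold once the condition is controlled by supplementation, which is slightly wider than 6.4.1. That does not change the answer on whether rechallenge is allowed.

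**Extent of the conflict.**
- Combinations covered: 3 events × 2 grades = 6.
- Pointer agrees with the appendix: 2 thyroid events × 2 grades = 4 (4/6 = 67%).
- Pointer conflicts: 1 event × 2 grades = 2 (2/6 = 33%).

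**Maximum returns to dosing after Grade 3/4 hepatitis.**
- Under 6.4.1: 1 (first event) + 1 (second event) + 0 (third event, stop) = 2.
- Under Appendix 13.5: 0.

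**Does any sentence rank the two?**
1. The scope statement in 6.4 confines 6.4.1 to events not specified later. Hepatitis is specified later, in 6.4.2, but that row itself points dosing back to 6.4.1. The statement is circular here, and it does not mention the appendix.
2. The cell moves from general recommendations to specific guidelines. That suggests the specific text governs, but it is not worded as an exception.
3. Rechallenge under 6.4.1 is granted in the thyroid rows of the appendix and absent from the hepatitis rows. This too points to the appendix as the intended rule, by inference.
4. The appendix table carries the column header "Camidanlumab Tesirine Management Guideline", the same as the 6.4 tables. This argues against reading the appendix as supportive care only, but no sentence excludes that reading.

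The SAP does not address the point.

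**Patients affected.** This cannot be computed. The documents give no hepatitis rate, and hepatitis is not among the Grade 3 or higher Phase 1 events that Section 1.3 lists as seen in at least 5% of cHL patients.

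**The case against.** The strongest reply is that the row answers itself. A general rule followed by a specific one that names the event is ordinary drafting. The general pointer is still needed because the row is open-ended and covers endocrinopathies with no appendix entry. The protocol's own steroid and monitoring instructions for Grade 3/4 hepatitis are in Appendix 13.5, where the order to stop comes before the steroid lines.

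Nor does 6.4.1 ever compel re-treatment. Section 6.4 says: "Resumption of dosing with camidanlumab tesirine after any suspension, even when longer than 21 days, is at the discretion of the Investigator". A site that stops permanently therefore breaches nothing. The conflict is between a permission and a prohibition, and a compliant course always exists.

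There are also safeguards:

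- Autoimmune hepatitis is an adverse event of special interest (Section 8.1.1), reportable within 24 hours if serious and 48 hours if not (Section 8.2).
- Each confirmed Grade 3 or higher potentially immune-mediated toxicity makes the sponsor recalculate the study-wide incidence, and more than 10.0% pauses enrollment (Section 4.3).
- The iDSMB may meet on such events (Section 8.7).
- Liver injury meeting Hy's law is already a stop in the row above.

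Most of this stands. The intent can be inferred, and harm requires a site to overlook the second paragraph of the cell. But Investigator discretion makes the correct action available without making it required. The reporting and oversight provisions alert the sponsor without saying which dosing rule applies. The row still states a pointer that gives the wrong action for a safety stop.

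**Conclusion.** The concern holds. The 6.4.2 row, read as written, allows re-treatment after Grade 3 or 4 autoimmune hepatitis; the appendix it cites forbids it; and no sentence gives precedence. The conflict is confined to 2 of the 6 Grade 3 and 4 combinations in Appendix 13.5.

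The difference of at most two returns to dosing against none is a bound. It assumes the appendix is missed at both events and is not an expected effect. The conclusion also takes the appendix as the intended rule, which the context supports.

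This should be corrected, because a stopping rule for patient safety ought not to rest on inference. It has no bearing on sample size, the endpoints or the primary response-rate analysis in the all-treated population.

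**What to change.** In the autoimmune row of Section 6.4.2, qualify the pointer along these lines: *modify dosing per Section 6.4.1 except where Appendix 13.5 specifies otherwise; Grade 3 or 4 autoimmune hepatitis requires permanent discontinuation.* Send sites a clarification letter saying the same.

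Leave the thyroid rows as they are, since their return to 6.4.1 is correct. Add no rule for other liver-enzyme elevations: the appendix's referral of asymptomatic liver-test elevations and Hy's law to 6.4.2 stays as written. Sites will still have to judge whether a Grade 3 event is hepatitis or an isolated enzyme rise, which has its own hold-and-resume row. The edit does not address that.

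The cost is one phrase and a letter. Under Section 11.7 the phrase needs an amendment approved through the usual process. With the exception written in, re-treatment after Grade 3/4 autoimmune hepatitis falls plainly under item 3 of SAP Section 4.3, and the SAP needs no change.
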